###### **Bayesian Approach**

The Bayesian analysis will be conducted as a virtual adaptive study. The interim look dataset will be constructed as it would have been available after the 360th patient was enrolled, and the additional enrollment will be computed. The final analysis will be conducted using only the data from the interim and additional enrollment, along with the historical prior data, to simulate the results of an adaptive study.

##### **Methodology**

Historical data from the Attain Stability and Attain Performa Clinical studies will be incorporated using the power prior methodology with a discount function. A maximum weight of 37 effective patients will be

---

 Haddad, Tarek, et al. "Incorporation of stochastic engineering models as prior information in Bayesian medical device trials." *Journal of Biopharmaceutical Statistics* (2017): 1-15.

given to the historical data, equal to the number of subjects in the Attain Stability OUS study that had follow up data at six months or longer with an Attain Stability lead. Historical data will be scaled to create an effective weight of 37 patients in the case of the Attain Performa historical data because the actual study enrolled 401 patients.

The Attain Stability data will be applied only to complications associated with lead fixation: dislodgement and perforation. There were 0 events for 37 patients in the Attain Stability study. The Attain Performa data will be applied to all other complications. There were 10 non-fixation complications in the Attain Performance study, out of 401 patients.

There are three steps in the methodology:

1. Compare the historical and current data to create a measure of similarity,  $p$
2. Compute the effective sample size  $a_0$  of the historical data using a discount function based on the level of similarity
3. Combine the historical data  $y_0$  and current data  $y$  using the calculated weight  $a_0$  to get the combined data set  $y + a_0y_0$

These three steps are performed at the interim analysis and at the final analysis.

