### Comparison

Let  $y$  and  $y_0$  be the number of events that occur for the current data and historical data respectively and let  $n$  and  $n_0$  be the total number of subjects for the current and historical studies that reach the 6 month time point or had an event. A discount function is used to adjust the strength of the prior according to the agreement between current and historical data.

Suppose we develop the posterior distribution of  $\tilde{\theta}$  and  $\theta_0$  for the current data and historical data, respectively, both with minimally informative priors. Calculate  $\theta$  as:

$$\tilde{\theta} \sim \text{beta}(y + 1, n - y + 1) \quad (1)$$

$$\theta_0 \sim \text{beta}(y_0 + 1, n_0 - y_0 + 1) \quad (2)$$

We can stochastically compare the distribution of  $\tilde{\theta}$  to  $\theta_0$  as follows:

$$p = P(\tilde{\theta} \leq \theta_0 | y, n, y_0, n_0) \quad (3)$$

Equation (3) can be calculated by drawing  $m$  samples of  $\tilde{\theta}$  and  $\theta_0$  from (1) and (2) (i.e.  $\tilde{\theta}^1, \tilde{\theta}^2 \dots \tilde{\theta}^m$  and  $\theta_0^1, \theta_0^2 \dots \theta_0^m$  )

$$p = P(\tilde{\theta} \leq \theta_0) = \frac{1}{m} \sum I\{\tilde{\theta}^i < \theta_0^i\}$$

The resulting p-value is then used to compute the discount function.

[figure not shown]

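### The 37 and the 401 used as historical denominators in the Bayesian analysis of Secondary Objective #2 are not described on the SAP's own definition of n0

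*SAP*

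**What the plan says.** SAP 7.8.4 borrows from two earlier studies with a discounted power prior.

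- **Definition.** Under Comparison, n and n0 are to "be the total number of subjects for the current and historical studies that reach the 6 month time point or had an event". One definition covers the current data and both historical studies.
- **Fixation history.** Under Methodology, the maximum weight of 37 is the number of "subjects in the Attain Stability OUS study that had follow up data at six months or longer with an Attain Stability lead". The input is stated as "There were 0 events for 37 patients in the Attain Stability study", and it is "applied only to complications associated with lead fixation: dislodgement and perforation".
- **Other failure modes.** The input is stated as "There were 10 non-fixation complications in the Attain Performance study, out of 401 patients". Scaling down to 37 is needed "because the actual study enrolled 401 patients", and the discount-function table fixes the factor 37/401.
- **Status.** The Analysis Dataset text of 7.8.4 makes the frequentist estimate primary. Its denominator, Analysis Set #3 in 7.1.3, keeps subjects whose lead failed before 6 months.

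**The concern.** Neither historical count is described the way n0 is defined, and the two depart from it differently. The 37 is described as completers with no allowance for early events. The 401 is described as everyone enrolled, with no condition on reaching 6 months.

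The first gap matters more because of where the 0/37 is used. Dislodgement and perforation can end follow-up with the lead before six months. If inclusion requires six months with an Attain Stability lead, a subject whose lead was removed after such an event falls outside the 37. That subject would be counted under the n0 definition, and the equivalent subject in the current study is counted in Analysis Set #3.

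At stake are the point estimate and credible interval for the fixation modes, which would be pulled down. To a lesser degree, the number of effective historical patients counted towards the 400 would also be affected. For Performa, an enrolled denominator would dilute the historical rate. In addition, the 10 is worded as a count of complications, whereas the beta-binomial formula needs a count of subjects.

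**Working it through.** **The SAP's own figures.** 400 − 37 = 363, the minimum enrolment given under Interim analysis. (37/401) × 401 = 37, the Performa cap. Both reproduce.

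**Formulas (Comparison, discount function and combination steps of 7.8.4).**
- p = P(θ_current ≤ θ_0), with θ_current ~ beta(y+1, n−y+1) and θ_0 ~ beta(y0+1, n0−y0+1)
- discount factor d = 1 − exp(−(5p)²); â0 = d for Attain Stability and (37/401)·d for Performa
- posterior beta(α, β), with α = y + â0·y0 + 1 and β = (n−y) + â0·(n0−y0) + 1; mean α/(α+β)

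**Assumptions.** Current n = 363, the SAP's minimum. The current event counts, and the number of early-event subjects outside the 37, are not in the SAP and are varied here. Each added subject raises both y0 and n0 by one.

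**Fixation modes, 8/363 current events (2.2%).**

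| History | p | d | Posterior mean | 95% CrI |
|---|---|---|---|---|
| 0/37 | 0.405 | 0.98 | 9/401.4 = 2.24% | 1.03–3.90 |
| 1/38 | 0.749 | 1.00 | 10/403 = 2.48% | 1.20–4.21 |
| 2/39 | 0.915 | 1.00 | 11/404 = 2.72% | 1.37–4.52 |
| none | – | – | 9/365 = 2.47% | 1.14–4.28 |

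One omitted event would cancel the reduction that borrowing gives, and two would reverse it. Holding the weight at 37 instead of 38 or 39 hardly changes this: (8 + 37/38 + 1)/402 = 2.48% and (8 + 2 × 37/39 + 1)/402 = 2.71%.

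**Weight given to 0/37.**

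| Current events /363 | p | d | Effective patients |
|---|---|---|---|
| 4 (1.1%) | 0.607 | 1.00 | 37.0 |
| 7 (1.9%) | 0.449 | 0.99 | 36.8 |
| 11 (3.0%) | 0.298 | 0.89 | 33.0 |
| 15 (4.1%) | 0.198 | 0.62 | 23.1 |
| 22 (6.1%) | 0.095 | 0.20 | 7.5 |

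Because p is one-sided, adding historical events raises the weight: at 15/363, d is 0.62 with 0/37 and 0.998 with 1/38.

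**Performa.** How many of the 401 reached 6 months or had an event is not given. For illustration only, this trial's planned 15% attrition gives 401 × 0.85 ≈ 341. The historical rate then moves from 10/401 = 2.49% to 10/341 = 2.93%.

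| Current events /363 | d, n0 = 401 | d, n0 = 341 | Mean, n0 = 401 | Mean, n0 = 341 |
|---|---|---|---|---|
| 9 | 0.998 | 1.00 | 2.72% | 2.76% |
| 15 | 0.24 | 0.64 | 4.34% | 4.30% |

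The 341 columns use the factor 37/341, so that the cap stays at 37. At 15/363 the borrowed weight goes from 0.239 × 37 ≈ 9 to 0.638 × 37 ≈ 24 effective patients. With the factor left at 37/401 it would be about 20.

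**The case against.** The strongest reply is that no input is shown to break the definition. If no fixation event occurred in the earlier study, then reaching 6 months and reaching 6 months or having an event select the same people, and 0/37 is correct. The phrase about six-month follow-up explains the size of the cap and is not worded as an exclusion rule. A subject whose lead was repositioned, or replaced with the same type, could still be among the 37. Likewise, the word enrolled appears only in the sentence explaining why Performa is scaled. All of this stands, and it limits the point to a mismatch of stated definitions with a possible bias.

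Two stronger readings are tempting. A reader might infer that the history is event-free by construction. The SAP does not support that, because it gives neither the size of the earlier study nor its early events or lead removals. A reader might also infer that the absence of events is what earns the history a high weight. The formula works the other way: among the histories compared, 0/37 receives the lowest weight, and its weight falls further once the current rate passes about 3%.

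The consequences are also modest. SAP 4.2 sets no performance requirement for the secondary objectives, and the adaptive study is reconstructed retrospectively, so planned enrolment stays at 471. None of this reconciles the two descriptions, and as written the SAP cannot tell a reader whether early failures were counted in the 37.

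**Conclusion.** The point holds as an internal inconsistency in 7.8.4 that should be corrected. The described bases of the 37 and the 401 do not match the n0 definition given in the same section. For the fixation modes the mismatch runs in a direction that could understate the failure rate. The plausible size is about a quarter of a percentage point on the posterior mean per omitted event (2.24% to 2.48% at 8/363), with widely overlapping credible intervals. This rests on assumed current counts and an assumed number of omitted subjects; whether any were omitted is unknown.

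For Performa the estimate barely moves. The borrowed weight can change noticeably when the current rate is above the historical one, but only under an assumed n0. No primary result depends on either input.

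**What to change.** - Re-count y0 and n0, in subjects, for both historical studies on the definition under Comparison. Include anyone with a qualifying event before 6 months, even if the lead was removed.
- State the resulting y0/n0 in 7.8.4.
- If they change, update the cap of 37, the factor 37/401 and the figure of 363 to match.
- If the re-count confirms 0/37 and 10/401, one sentence saying that both meet the n0 definition closes the point.

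The cost is a re-count of two datasets the analysis already uses and a short SAP edit. The historical record may look slightly less favourable as a result.

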### Comparison

Let  $y$  and  $y_0$  be the number of events that occur for the current data and historical data respectively and let  $n$  and  $n_0$  be the total number of subjects for the current and historical studies that reach the 6 month time point or had an event. A discount function is used to adjust the strength of the prior according to the agreement between current and historical data.

Suppose we develop the posterior distribution of  $\tilde{\theta}$  and  $\theta_0$  for the current data and historical data, respectively, both with minimally informative priors. Calculate  $\theta$  as:

$$\tilde{\theta} \sim \text{beta}(y + 1, n - y + 1) \quad (1)$$

$$\theta_0 \sim \text{beta}(y_0 + 1, n_0 - y_0 + 1) \quad (2)$$

We can stochastically compare the distribution of  $\tilde{\theta}$  to  $\theta_0$  as follows:

$$p = P(\tilde{\theta} \leq \theta_0 | y, n, y_0, n_0) \quad (3)$$

Equation (3) can be calculated by drawing  $m$  samples of  $\tilde{\theta}$  and  $\theta_0$  from (1) and (2) (i.e.  $\tilde{\theta}^1, \tilde{\theta}^2 \dots \tilde{\theta}^m$  and  $\theta_0^1, \theta_0^2 \dots \theta_0^m$  )

$$p = P(\tilde{\theta} \leq \theta_0) = \frac{1}{m} \sum I\{\tilde{\theta}^i < \theta_0^i\}$$

The resulting p-value is then used to compute the discount function.

[figure not shown]
### Compute the discount function

The weight of the historical data will be computed with a discount function based on the measure of similarity  $p$ . The historical data will be scaled from 0 to 37 effective patients as:

Prior weight from Attain Stability	Prior weight from Attain Performa
------------------------------------	-----------------------------------

$\hat{a}_0 = 1 - e^{-(p*5)^2}$	$\hat{a}_0 = \frac{37}{401} [1 - e^{-(p*5)^2}]$
--------------------------------	---

The discount function for the Attain Stability data set is given below:

**Figure 2: Loss function  $\hat{a}_0 = 1 - e^{-(p*5)^2}$**

### Combine the current and historical data

Let  $y$  and  $y_0$  be the number of events that occur for the current data and historical data respectively and let  $n$  and  $n_0$  be the total number of subjects for the current and historical studies that reach the 6 month time point or had an event. Following the work of Ibrahim and Chen [1], the posterior probability for event rate  $\theta$  using the power prior is given as:

$$P(\theta|y, n, y_0, n_0, \hat{a}_0) = \text{beta}(\alpha, \beta)$$

where

$$\alpha = y + \hat{a}_0 y_0 + 1$$

$$\beta = (n - y) + \hat{a}_0 (n_0 - y_0) + 1$$

### Interim analysis

This analysis will be conducted with data retrospectively analyzed as it would have been available for the first consecutively enrolled 360 subjects. Within this data set, some patients will not have completed the full evaluation period. A longitudinal model will be employed to enable final observations to be imputed for those subjects with incomplete information.

There are 3 types of subjects at a given interim analysis:

1. Subjects that have complete data
2. Subjects that have partial data (censored value at a particular time)
3. Subjects that have no information (subjects that have not been enrolled)

We will construct predictive probabilities for types 2 and 3. The predictive probability model that will be used is a piecewise exponential. This will allow us to impute final outcomes for the subjects who have not had an event and have not completed 6 month follow up.

We assume a gamma distribution prior for each of the exponential segments, which allows us to estimate the hazard rate using closed form conjugacy. Therefore, the posterior is also a gamma distribution.

We partition duration time into 3 intervals across six months (0-2, 2-4, and 4-6 months) and assume the hazard is constant within each interval. The event times are therefore modeled as:

$$T_{\text{event}} \sim \text{PE}(\lambda_1, \lambda_2, \lambda_3)$$

where  $\lambda_1, \lambda_2, \lambda_3$  are the hazards for the three segments.

The purpose of the interim look is to determine the number of additional patients to enroll in order to have a high probability of meeting the required effective sample size of  $n_{\text{effective}} = 400$  (after accounting for attrition). The effective sample size is the sum of enrolled patients and effective historical patients at the final analysis. The interim analysis may result in as few as 363 patients enrolled. This study follows methods from Berry, et.al.

Adaptive Bayesian sample size algorithm:

1. If the predictive probability of  $n_e \geq 400$  is larger than 80% then enrollment will stop.
2. If the predictive probability of  $n_e \geq 400$  is less than 80%, enroll sufficient additional patients to make the probability of  $n_e \geq 400$  at least 80%.

### **Final Analysis**

The final analysis will be performed using the 6-month data from the patients enrolled at the interim analysis time point, along with the 6-month data from the number of additional patients resulting from the interim analysis. The same three steps (Compare, Compute, Combine) will be performed to incorporate the historical data sources.

The estimates for rates of lead failure modes will be presented as a point estimate and 95% credible intervals.

### **7.8.5. Secondary Objective #3**

The third secondary objective aims to estimate electrical measurement values (PCTs and Lead Impedance) at 6 months post-implant.

#### **Analysis Dataset:**

Analysis set #2 per section 7.1.3.

#### **Analysis Method:**

Mean, standard deviation, minimum, median and maximum for PCTs and lead pacing impedance at the 6-month follow-up visit will be presented for the final programmed LV lead pacing polarity. In addition, the frequency of each LV lead pacing polarity being used at the final programmed configurations will be presented.

Electrical values may be collected via eCFR and Save-to-Media files (i.e. Save-to-Diskette and Carelink Transmissions). The statistical analysis will prioritize documented values from eCRF over save-to-media data. If discrepancies of over 1 volt is identified comparing values from two data sources, data queries may be initiated for resolution.

## **8. Validation Requirements**

Minimum validation requirements for the programs written to execute the analyses in this SAP:

---

 S.M. Berry, B.P. Carlin, J.J. Lee, P. Muller, Bayesian adaptive methods for clinical trials. CRC press, 2010.

- Primary objective: Level II
- Secondary objectives: Level II
- Description of patient population (baseline demographics, patient characteristics, etc.): Level II
- Deviation table and listing: Level III
